Aim 2a. To evaluate possible mechanism(s) by which azithromycin may affect morbidity and mortality, by comparing reasons for re-hospitalization, prevalence of pathogen carriage, and markers of enteric dysfunction between the randomization arms. We calculated the minimum detectable association between treatment arm and cause-specific re-hospitalizations (hospitalization due to diarrhea, acute respiratory infection, malnutrition, or malaria vs. any other) among enrolled children, assuming an alpha level of 0.05, power of 0.80, and a ratio of treatment to placebo of 1:1. Based on data from Kenya, re-hospitalization rates due to specific causes ranged from approximately 0.5% to 5.7% in the 6 month post-discharge period, with the lowest rate reported for gastroenteritis and the highest for malaria.[9] By not conditioning on the child having the same diagnosis at initial hospitalization, we expect the cumulative incidence of cause-specific re-hospitalizations to range from 2.5% to 10%. With this range of outcome rates, we will be able to detect hazard ratios of 0.48 to 0.70 for the effect of azithromycin on specific severe morbidities.

Among the 1400 children in whom nasopharyngeal swabs and stool samples are cultured, we expect 56% of children in the placebo group to have *S. pneumoniae* identified based on data from Kenya, providing $\geq 80\%$ power to detect a prevalence ratio of 0.85 (or 1.15) between the two treatment arms at each time point.[51-53] Because there is a strong link between carriage of *S. Pneumoniae* and development of associated disease, and because empiric azithromycin has been shown to prevent reduce clinical pneumonia by as much as 75% in an outbreak setting, we believe that our ability to detect a 15% reduction in risk is appropriately sensitive.[54, 55] Based on prevalence of *Salmonella* spp., *Shigella* spp., *Campylobacter* spp., or diarrheagenic *E. coli* (ETEC, EHEC, EPEC, and EAEC) among asymptomatic children in Western Kenya, we expect 20% of children in the placebo group to have a bacterial pathogen isolated at each time point, resulting in $\geq 80\%$ power to detect differences in enteric pathogen prevalence of 0.68 (1.36) at each time point.[48]

Figure 6. Power and detectable hazard ratios given a range of mortality rates

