Aim 2a. To evaluate possible mechanism(s) by which azithromycin may affect morbidity and mortality, by comparing reasons for re-hospitalization, prevalence of pathogen carriage, and markers of enteric dysfunction between the randomization arms. To evaluate the association between azithromycin and rate of cause-specific re-hospitalizations (hospitalization due to diarrhea, acute respiratory infection, malnutrition, or malaria) we will use Anderson-Gill proportional hazards modeling with previous re-hospitalizations included as time-dependent covariates in the model to capture the dependent structure of recurrence times. Because we will not have granularity in the time points other than 90-days and 6-months for assessment of pathogen carriage, we will compare the prevalence of pathogen carriage at 90-days and 6 months by randomization arm using generalized estimating equations (GEE) with a Poisson link, exchangeable correlation structure, and will adjust for baseline presence of a bacterial pathogen. To determine whether an observed association between the intervention and pathogen carriage wanes over time, we will test the hypothesis that the prevalence ratios comparing carriage in intervention arms are the same at the two follow-up time points using a chi-squared test. For the random subgroup of children in the **Enteric Function Cohort**, we will create a composite disease activity score ranging from 0 to 10 as previously described.[63] We will model the mean composite intestinal inflammation score by treatment group using linear regression. If the baseline comparison of randomization arms reveals an imbalance in characteristics between the treatment groups, we will additionally adjust for these variables, including post-discharge antibiotic use, in the regression models. Additionally, we will compare baseline differences between children randomized into the **Enteric Function Cohort** to those who were not, in order to evaluate representativeness of the random sample.

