All enrolled children	Time to re-hospitalization (due to diarrhea, pneumonia, malaria, malnutrition)	Randomization arm (ITT primary and per-protocol secondary)	1) Site 2) adjusting for imbalanced baseline factors	Anderson-Gill
Enteric and nasopharyngeal pathogens				
All enrolled children	Prevalence of Shigella , Salmonella , Campylobacter , Cryptosporidium , Giardia @ 0, 3, & 6	Randomization arm (ITT primary and per-protocol secondary)	1) Site 2) adjusting for imbalanced baseline factors & baseline presence of pathogen	GEE with Poisson link & exchangeable correlation structure
	Streptococcus pneumoniae prevalence @ 0, 3, & 6	Randomization arm (ITT primary and per-protocol secondary)	1) Site 2) adjusting for imbalanced baseline factors & baseline presence of pathogen	GEE with Poisson link & exchangeable correlation structure

Aim 2b. To determine whether empiric administration of azithromycin at hospital discharge increases risk of antimicrobial resistance in commensal *E. coli* and pneumococcal isolates from treated children and their household contacts.

Population	Dependent variable	Independent Variable	Covariates	Statistical model
Resistance in enrolled children				
1. Random subset of enrolled children selected to be in the AMR sub-study 2. Children in AMR sub-study in whom E. coli was isolated	Prevalence of resistance to azithromycin and presence of extended spectrum beta-lactamase-producing E. coli . In secondary analyses, prevalence of ampicillin, chloramphenicol, ciprofloxacin, ceftriaxone, ceftazidime, gentamicin, trimethoprim-sulfamethoxazole @ 0, 3, & 6 months	Randomization arm (ITT primary and per-protocol secondary)	1) Site 2) Adjusting for imbalanced baseline factors & baseline presence of resistance 3) Adjusting for propensity score made up of factors predictive of likelihood that E. coli is isolated	GEE with Poisson link & exchangeable correlation structure. Wald tests to compare between arms and to test for time-interaction (waning in resistance from 3 to 6 months in AZM arm)
Resistance in household contacts				

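### The SAP's Aim 2a carriage rows omit the protocol's test for waning between 90 days and 6 months and leave visit-specific ratios unspecified

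*Protocol*

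**What the plan says.** Protocol, Data Analysis, Aim 2a: "we will compare the prevalence of pathogen carriage at 90-days and 6 months by randomization arm using generalized estimating equations (GEE"), with adjustment for baseline presence of a bacterial pathogen. To see whether any association fades, "we will test the hypothesis that the prevalence ratios comparing carriage in intervention arms are the same at the two follow-up time points" by a chi-squared test. Protocol, Sample Size, Aim 2a states its carriage power for pneumococcus as a contrast "between the two treatment arms at each time point", and powers enteric pathogens per time point as well.

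SAP Section 6, Aim 2a table, both carriage rows:
- Independent variable: "Randomization arm (ITT primary and per-protocol secondary").
- Covariates: site, then "adjusting for imbalanced baseline factors & baseline presence of pathogen".
- Outcome times, here from the pneumococcus row: "prevalence @ 0, 3, & 6". The enteric row lists the same three times.
- Model: "GEE with Poisson link & exchangeable correlation structure". The cell ends there.

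SAP Section 6, Aim 2b table: all four resistance rows use the same GEE description and then add "Wald tests to compare between arms and to test for time-interaction".

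The SAP's Outcome Definitions place bacterial carriage at the 90- and 180-day visits only. The revision history does not mention the carriage waning test.

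**The concern.** The protocol plans a waning test for both carriage and resistance. The SAP carries it forward for resistance only and gives no reason. An exchangeable working correlation has a role only when visits are modelled together, and a joint model with arm but no arm-by-visit term yields one arm ratio across visits. An analyst who fits the rows literally would therefore lose a protocol-specified part of the mechanism aim, from data already collected.

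The role of month 0 is a second gap. The rows list it among the outcome times, the second covariate set adjusts for baseline pathogen, and the outcome definition leaves it out. If month 0 enters as an outcome, a visit at which no treatment effect is possible is averaged into the arm ratio.

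It also matters for multiplicity. SAP Section 4 applies Benjamini-Hochberg to the secondary aims, and the number of carriage tests depends on whether ratios are pooled or given per visit. That number is not fixed in advance.

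**Working it through.** **Inputs from the documents.** Placebo pneumococcal carriage 56% and detectable ratio 0.85; 1400 children cultured, 700 per arm (Protocol, Sample Size, Aim 2a). Loss to follow-up 20% (Protocol, Sample Size, Aim 3), so n = 700 × 0.8 = 560 per arm. Two-sided 0.05 (SAP Section 4), with no Benjamini-Hochberg adjustment here.

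**Assumptions.** 6-month ratio 1.00 (no effect left), 0.925 (half left) or 0.85 (all left); within-child correlation ρ from 0 to 0.4; equal weight for the two visits; month 0 not an outcome.

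**Step 1: reproduce the protocol's power.** p0 = 0.56, p1 = 0.56 × 0.85 = 0.476, mean 0.518.
Power = Φ[(0.084 − 1.96·√(2·0.518·0.482/560)) / √((0.56·0.44 + 0.476·0.524)/560)] = Φ[(0.0840 − 0.0585)/0.0298] = 0.804.
The stated power of at least 80% holds. The enteric figure (20% prevalence, ratio 0.68) gives 0.818 by the same method.

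**Step 2: the 90-day comparison on the log-ratio scale.** V90 = (1−p1)/(n·p1) + (1−p0)/(n·p0) = 0.001966 + 0.001403 = 0.003369, SE 0.0580. |ln 0.85| = 0.1625. Power = Φ(0.1625/0.0580 − 1.96) = 0.80.

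**Step 3: one pooled arm ratio over months 3 and 6.** Pooled log ratio = (ln R90 + ln R180)/2. Variance = (V90 + V180 + 2ρ√(V90·V180))/4. V180 is 0.002806, 0.003065 or 0.003369 for no, half or all of the effect left.

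**Step 4: the waning test.** Difference = ln R90 − ln R180. Variance = V90 + V180 − 2ρ√(V90·V180).

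| Effect left at 6 months | Pooled ratio | Pooled SE (ρ = 0 to 0.4) | Pooled power (ρ = 0.4 to 0) | Waning-test SE (ρ = 0 to 0.4) | Waning-test power (ρ = 0 to 0.4) |
|---|---|---|---|---|---|
| None (1.00) | 0.92 | 0.0393 to 0.0465 | 42–54% | 0.0786 to 0.0610 | 54–76% |
| Half (0.925) | 0.89 | 0.0401 to 0.0474 | 72–85% | 0.0802 to 0.0622 | 18–27% |
| All (0.85) | 0.85 | 0.0410 to 0.0486 | 92–98% | – | no waning to detect |

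**Step 5: check of the averaging.** Averaging the ratios instead of their logs gives (0.85 + 1.00)/2 = 0.925 when no effect is left, with 39–51% power. A simulated arm-only exchangeable Poisson GEE (100,000 per arm) gave 0.929. Both agree with the first row of the table.

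**Step 6: month 0 as an outcome.** The ratio moves to (1 + 0.85 + 1.00)/3 = 0.95 with no effect left, (1 + 0.85 + 0.925)/3 = 0.925 with half left, and (1 + 0.85 + 0.85)/3 = 0.90 with all left. Full persistence no longer protects against dilution.

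**The case against.** The strongest reply is that the SAP never says the visits are pooled. Carriage is listed at three times, SAP Table 1 gives separate windows for day 90 and day 180, and the outcome definition names both visits, so per-visit ratios fit the text as well. The Aim 2b rows also list no visit term in their independent-variable or covariate columns and yet test a time interaction, so those columns do not enumerate every model term. This stands. A reader might infer that the SAP prescribes a single averaged ratio, and the documents do not support that. Nor is arm the only term, since site and baseline covariates are listed.

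A second reply concerns the hypotheses. The Aim 2a hypothesis is lower carriage over the 6 months as a whole, which an overall arm ratio can address. Only the Aim 2b hypothesis predicts a difference at 90 days that has gone by 6 months. This also stands: the protocol asks whether a carriage association wanes and does not say that it expects so.

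A third reply is that pooling can help. If half the effect persists, pooled power is close to that of the 90-day comparison; if all of it persists, pooled power is higher.

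None of this supplies the missing test. Under either reading of the rows, the protocol's comparison of the two ratios is absent from the SAP's carriage plan.

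**Conclusion.** The concern holds as an omission and an under-specified estimand in a secondary aim. The protocol commits to a comparison at two visits and a test that the two ratios are equal; the SAP carriage rows state neither, and the role of month 0 is inconsistent. The SAP nowhere withdraws the test, so a deliberate decision to drop it should not be inferred.

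The size is conditional on the rows being run as an arm-only joint GEE over months 3 and 6. A reader might infer that a 90-day effect is halved. That needs no effect at all at 6 months and equal visit weights, and the documents give no 6-month carriage effect. Over the assumed range, power runs from roughly half, through about equal, to well above the 80% of the 90-day comparison. What is lost in every case is the answer to the waning question. The power figures are approximate and unadjusted for multiplicity. The primary endpoint is not affected.

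**What to change.** In both carriage rows of the SAP's Aim 2a table:
- model months 3 and 6 as the outcomes, with month 0 as a baseline covariate only, in line with the outcome definition;
- add visit and arm-by-visit terms;
- report the prevalence ratio at each visit;
- give a Wald test of arm-by-visit from the same GEE as the waning test, which uses the within-child correlation.

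An overall arm ratio may be reported as well. If the waning test is not wanted, the SAP should say so and why.

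The cost is a few words in two table rows and no new data. The Benjamini-Hochberg family grows: the rows name six organisms, so one pooled ratio each is 6 comparisons, while two visit ratios and one waning test each are 6 × 3 = 18. The waning test is also weak under partial waning (about 18–27% power if half the effect remains, 54–76% if none does), so a non-significant result should not be read as showing a stable effect.

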Many children in sub-Saharan Africa who seek medical care suffer recurrent illness and/or death in the immediate period after the health care encounter. Although accessing health care interventions can reduce immediate risk, recurrent morbidity and mortality among those children who survive hospitalization remains extremely high. Illness following discharge from hospital is often the result of preventable and treatable infectious diseases. Additionally, many hospitalized children with underlying comorbidities are not being diagnosed with these comorbidities or experience delays in the initiation of care and treatment. As such, the administration of antibiotics to all children at hospital discharge may be particularly effective among those children with underlying comorbid conditions. Therefore, targeted antimicrobial interventions to cover residual infection, reduce carriage of pathogens, and provide prophylaxis against common exposures may significantly impact infectious morbidity and mortality in the post-discharge period.

Although some progress has been made in decreasing child mortality over the last decade in parts of SSA, it is unlikely that the global community will meet child mortality targets stated in the Millennium Development Goals without additional effective interventions.[6, 13, 14]. Therefore, novel interventions targeting highest risk individuals are urgently needed to reach these goals. Our study aims to reduce post-discharge re-hospitalizations and mortality, to explore possible mechanisms by which azithromycin has benefit and risk, and to identify correlates and intermediate markers of re-hospitalization and death in the post-discharge period as a novel intervention towards decreasing child mortality.

STUDY OBJECTIVES

Primary Aims

Aim 1. To compare rates of **re-hospitalization and mortality** in the 6 months following hospital discharge among Kenyan children receiving 5-day azithromycin vs. placebo.

Hypothesis: The provision of a 5-day course of azithromycin provided at discharge will reduce hospital re-admission and death within the 6 months following discharge, as compared to placebo.

Aim 2a. To evaluate possible **mechanism(s)** by which azithromycin may affect morbidity and mortality, by comparing **reasons for re-hospitalization, prevalence of pathogen carriage, and markers of enteric dysfunction** between the randomization arms.

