Stool (rectal swabs), nasopharyngeal swabs and DBS will be collected as described above and undergo laboratory testing as described in Table 5. All biological samples will be collected by staff trained in biosafety and GCLP. Samples will be processed in Kenya when technology is available at one of the following laboratories: Kenya Medical Research Institute (KEMRI) (Wellcome Trust or Centre for Microbiology Research [CMR]) or at the University of Nairobi (Microbiology Department). Metagenomic analyses and/or analyses that require technology not available in Kenya will be performed at the University of Washington. If stool culture results report *Shigella* infection, the study staff will contact the child's caregiver and encourage the caregiver to bring the child back for treatment if the child is symptomatic.

Table 5. Laboratory testing of stool, nasopharyngeal swab and blood specimens collected from participants at enrollment, 90-days, and 6 months

Specimen Collected	Participants	Purpose	Tests Performed
Stool/ flocked rectal swabs	All enrolled children and adults in the Close Contact Cohort	Bacterial ID and storage for AST	Fresh or frozen stool samples/rectal swabs will be evaluated for enteric bacteria and antimicrobial susceptibility testing (AST) will be performed using standard microbiologic or molecular diagnostic protocols. Colonies of Escherichia coli (E.coli) and other enteric pathogens will be stored for future microbiologic or molecular testing.
	All enrolled children	Parasite detection	Fresh or frozen stool will be tested for parasites using microscopy or antigen test kits such as ImmunoCard STAT! Cryptosporidium/Giardia (Meridian Bioscience, Inc), Xpect Giardia Cryptosporidium (Remel, Inc), Quik CheK or similar tests on stored stool/rectal swab samples. If available, molecular testing will be performed.
	Children enrolled in Enteric Function cohort, and adults in the Close Contact Cohort	Enteric inflammation	Commercially available enzyme-linked immunosorbent assays such as neopterin (NEO), alpha-anti-trypsin (AAT), myeloperoxidase (MPO), or similar tests, will be used to measure enteric inflammation on fresh or frozen stool samples..

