A dedicated study data team will be responsible for all data entry, management and storage of study data. Each site will have a dedicated data clerk responsible for data entry and synchronization with the central server. The data team will be in close communication with the Seattle-based statistical team (under [name]) for reporting, monitoring, and analysis. Entered data will be synchronized with the central database system on a daily basis and verified by the Seattle-based data management team. RedCap allows study staff at different locations to directly enter and review data online, with a complete auditing trail system tracks changes to data, and allows numerous real-time built-in data validation/quality checks with prompts during entry to ensure accuracy.

Data Analysis

The primary study endpoint is a combined outcome of mortality and hospital readmission, as re-hospitalization is highly associated with risk of subsequent poor outcome. Additional analyses will be conducted individually for these two outcomes. The secondary endpoints of cause-specific morbidity (diarrhea, acute respiratory infection, malnutrition, or malaria), pathogen carriage in stool or nasopharyngeal swabs and markers of enteric dysfunction will be used to better elucidate the mechanism by which azithromycin may effect the primary endpoints of mortality and re-hospitalization.

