A short course of azithromycin given to children with recent severe illness being discharged from hospital may optimize benefit while reducing both individual and population level risks. Azithromycin may reduce post discharge morbidity and mortality through infection-related mechanisms such as treating undiagnosed, incompletely treated or nosocomial infections, or by protecting against new or recrudescent infections that occur during recovery. Azithromycin may also act through non-antimicrobial pathways by anti-inflammatory and/or immune-modulatory effects.

Objectives

Aim 1. To compare rates of **re-hospitalization and mortality** in the 6 months following hospital discharge among Kenyan children receiving 5-day azithromycin vs. placebo.

Hypothesis: The provision of a 5-day course of azithromycin provided at discharge will reduce hospital re-admission and death within the 6 months following discharge, as compared to placebo.

Aim 2a. To evaluate possible **mechanism(s)** by which azithromycin may affect morbidity and mortality, by comparing **reasons for re-hospitalization and prevalence of pathogen carriage** between the randomization arms.

Hypothesis: Children treated with azithromycin will experience fewer hospitalizations due to diarrhea, acute respiratory infection, and malnutrition, and will be less likely to have respiratory and gastrointestinal carriage of potentially pathogenic organisms, as compared to children treated with placebo in the 6 months following hospital discharge.

Aim 2b. To determine whether empiric administration of azithromycin at hospital discharge **increases risk of antimicrobial resistance** in commensal *Escherichia coli* (*E. coli*) and *Streptococcus pneumoniae* (*S. pneumoniae*) isolates from treated children and their household contacts.

*Hypothesis: Isolates of commensal *E. coli* and *S. pneumoniae* from children treated with azithromycin and their household contacts will have higher levels of macrolide and β -lactam resistance, compared to the placebo group, after 90 days of follow-up, but resistance in the 2 arms will be similar by 6 months.*

Aim 3. To identify **correlates and intermediate markers of post-discharge mortality and hospital readmission** among hospitalized Kenyan children.

Hypothesis: Children younger in age, with higher levels of bacterial pathogen carriage, immune dysfunction, and malnutrition will experience more frequent re-hospitalizations and deaths.

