Outcome	Azithromycin-treated group (N=)			Placebo-treated group (N=)			Effect Estimate		
	n	Person-time	Incidence rate (/100)	n	Person-time	Incidence rate (/100)	Hazard ratio	(95% CI)	p-value
Death or re-hospitalization									

In subgroup analyses, we will compare treatment effects in children whose caregivers report no additional antibiotic use over follow-up and separately, who report no additional azithromycin use specifically and in subsets of children defined by the following baseline characteristics: age, county of recruitment, HIV-exposure status, nutritional status, and discharge diagnosis. We will not conduct formal testing of interaction in these analyses. We will report within sub-group p-values but interpret as secondary sub-group analyses. Also in secondary analyses, we will allow more than one hospitalization and model the incidence of re-hospitalization by randomization arm using Anderson-Gill models.

We will report causes of death (and predisposing conditions in those deaths) by randomization arm (without statistical testing) as presented in Table 4.

Table 4. Causes of death by randomization arm

	Azithromycin-treated group (N=)	Placebo-treated group (N=)
Primary cause		
LRTI/Pneumonia		
Diarrhea		
Malaria		
Tuberculosis		
Other Infection		
Other non-infectious		
Predisposing conditions		
HIV		
Sickle cell disease		
Confirmed acquired condition		
Confirmed congenital condition		
None		

Statistical Analysis of Secondary Aims

In addition to the primary aim of the study to determine whether a short-course of azithromycin reduces risk of post-discharge morbidity and mortality, secondary aims include determining potential mechanisms and intermediate markers of an intervention effect, the impact of the antibiotic course on antimicrobial resistance in gut and nasopharyngeal pathogens, and correlates of post-discharge morbidity and mortality. The below tables outline these planned analyses.

Aim 2a. To evaluate possible mechanism(s) by which azithromycin may affect morbidity and mortality, by comparing reasons for re-hospitalization and prevalence of pathogens between the randomization arms.

Population	Dependent variable	Independent Variable	Covariates	Statistical model
------------	--------------------	----------------------	------------	-------------------

Reasons for re-hospitalization				

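### SAP v5.0 contains no analysis of the protocol's enteric-dysfunction endpoint and gives no reason, and the protocol's own model names no follow-up visit and leaves enrollment-score adjustment conditional

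*Protocol*

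**What the plan says.** **Protocol.** Aim 2a (Study Objectives) compares "reasons for re-hospitalization, prevalence of pathogen carriage, and markers of enteric dysfunction" between arms, and its hypothesis predicts less enteric dysfunction with azithromycin. The Sample Size section justifies an Enteric Function Cohort of 300 children, 150 per arm. The opening of Data Analysis lists the endpoint as secondary: "pathogen carriage in stool or nasopharyngeal swabs and markers of enteric dysfunction will be used to better elucidate the mechanism". Under Specimen collection, the cohort provides an extra portion of stool for inflammation testing at enrollment, 90 days and 6 months. Table 5, which lists the inflammation assays, has the same schedule: "Laboratory testing of stool, nasopharyngeal swab and blood specimens collected from participants at enrollment, 90-days, and 6 months".

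The analysis is in Data Analysis, Aim 2a. The markers are combined into a score from 0 to 10, and then: "We will model the mean composite intestinal inflammation score by treatment group using linear regression". Baseline variables are added only if the arms look imbalanced.

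**SAP v5.0.** The Aim 2a objective in Section 2 is reduced to "reasons for re-hospitalization and prevalence of pathogen carriage", and the Section 6 analysis table is introduced as "comparing reasons for re-hospitalization and prevalence of pathogens between the randomization arms". The Aim 3 hypothesis also omits enteric dysfunction, which the protocol's version includes: "Children younger in age, with higher levels of bacterial pathogen carriage, immune dysfunction, and malnutrition will experience more frequent re-hospitalizations and deaths".

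**The concern.** The two governing documents disagree on whether a named secondary endpoint exists. A cohort was sized and extra stool planned for it, and families consent on that basis. If the SAP is followed, one of the three mechanism comparisons in Aim 2a is not made, and a reader cannot tell whether it was abandoned, postponed or overlooked.

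If the analysis is done later from the protocol text alone, two choices stay open until data are in hand: which follow-up visit (or combination of visits) is tested, and whether the enrollment score enters the model. The carriage model in the same protocol section has neither gap. It names 90 days and 6 months and adjusts for baseline carriage.

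**Working it through.** **1. Where the endpoint appears**

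| Item | Protocol | SAP v5.0 |
|---|---|---|
| Aim 2a objective and hypothesis | Included | Absent (Section 2) |
| Aim 3 hypothesis | Included | Absent (Section 2) |
| Nested cohort | Enteric Function and Contact Cohorts, 1:5, 150 per arm | Contact cohorts only, 1:5, 150 per arm (Section 3, Randomization) |
| Visit windows | 90 days and 6 months for stool | No row for the score (Table 1) |
| Secondary endpoints | Listed | Absent (Section 6, Outcome Definitions) |
| Analysis | Linear regression by arm | No row (Section 6, Aim 2a table) |
| Reason for the difference | – | None in the revision history (Section 1) |

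The SAP is not limited to the primary aim. Section 6 sets out analyses for Aims 2a, 2b, 3 and 4, so its scope does not explain the gap. The revision history records smaller changes, such as shell tables and the definition of an overnight stay.

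**2. The plan's own sample size**

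Inputs (Protocol, Sample Size, Aim 2a): difference 2.8 mg/L, SD 7.8 mg/L, alpha 0.05, power 0.80, 1:1. The two-sided test is from SAP Section 4.

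n per arm = 2 × (1.960 + 0.842)² × 7.8² / 2.8² = 2 × 7.85 × 60.84 / 7.84 ≈ 122, or 244 in total. A t-test gives 123 per arm, or 246. The stated 250 reproduces.

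**3. Whether those inputs describe the analysed variable**

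The calculation is for a concentration in mg/L. The model is for a score bounded by 0 and 10. The largest SD such a score can have is (10 − 0)/2 = 5, reached only if half the children score 0 and half score 10. An SD of 7.8 is therefore impossible for the score. Power figures built on 2.8 and 7.8 would carry over only if the score had a similar standardized difference (2.8/7.8 = 0.36), and the documents give no information on that.

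**4. Precision forgone without the enrollment score**

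This ratio is unit-free. With correlation rho between enrollment and follow-up scores, adjustment multiplies residual variance by 1 − rho² and confidence interval width by sqrt(1 − rho²). The documents do not give rho, so the range is assumed.

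| rho (assumed) | 1 − rho² | CI width factor |
|---|---|---|
| 0.1 | 0.99 | 0.995 |
| 0.2 | 0.96 | 0.980 |
| 0.3 | 0.91 | 0.954 |
| 0.4 | 0.84 | 0.917 |
| 0.5 | 0.75 | 0.866 |

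The interval narrows by between 0.5% and 13%. The enrollment sample is taken at discharge from an acute admission and the outcomes follow 90 days and 6 months later in children aged 1 to 59 months, so the low end is plausible.

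**The case against.** - **The protocol is itself a plan.** It names the cohort, the score and the model, so it would be wrong to say that a later analysis has no prior specification. This stands. The plan is thin, because it fixes neither the visit nor the covariates, but it exists.
- **A separate, later analysis may be intended.** The protocol stores stool for eventual inflammation testing, and the SAP's first report covers only the primary aim. This is possible, but the SAP specifies the other secondary aims and says nothing about deferring this one.
- **Removal from the SAP is not shown.** A reader might infer that the endpoint was in an earlier SAP and was silently deleted. Only v5.0 is available, and secondary-aim analyses entered at v2.0. If no SAP version ever held the endpoint, no revision entry was due. A record elsewhere is also possible. What the documents show is an unexplained mismatch between protocol and SAP.
- **Baseline adjustment is a refinement.** Randomization makes the unadjusted comparison unbiased, and the enrollment score could enter under the imbalance rule. Both points stand. The rule does not guarantee the precision gain, however, because it depends on what the data show. The contrast with carriage is also weaker in the SAP, where baseline pathogen presence appears only in the second covariate set, after site alone.
- **Adding a second visit need not help.** With an arm-by-visit term, each visit-specific effect gains almost nothing from the other visit unless data are missing. A gain would come through a visit-averaged contrast, and its size has not been computed.

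**Conclusion.** The mismatch is certain on the documents: the protocol has a secondary endpoint with a dedicated 300-child cohort, and SAP v5.0 has neither the endpoint nor a reason for its absence. Followed as written, the SAP leaves that Aim 2a comparison unmade.

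The modelling point is smaller. The protocol's regression is unbiased but names no visit and does not commit to the enrollment score. The cost is precision only: interval widths 0.5% to 13% larger than they need be, relative to the unadjusted width, for an assumed rho of 0.1 to 0.5.

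A reader might go further and read a power gain off the protocol's inputs. With 120 per arm (300 less 20%), 2.8 and 7.8 give 79.4% unadjusted, and 83.0% or 89.4% at rho 0.3 or 0.5. The arithmetic is right but the documents do not support the conclusion, because those inputs cannot describe the 0–10 score and rho is not given. Nor do they show that the enrollment score is the strongest covariate available. This is a secondary mechanistic endpoint and the primary analysis is unaffected.

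**What to change.** Before unblinding, do one of two things.

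1. **Specify the endpoint in the SAP.** Restore it to Aim 2a, the secondary endpoints, the visit-window table and the Aim 2a analysis table, and name the Enteric Function Cohort under Randomization. Model the 90-day and 6-month composite scores linearly on arm, visit, arm-by-visit, enrollment score and site, with enrollment score and site always included and within-child correlation allowed for. Name the contrast to be tested, for example the visit-averaged arm difference. Include it in the Benjamini-Hochberg adjustment that SAP Section 4 applies to all secondary aims.
2. **Record the removal.** If the assays will not be run, enter the decision in the SAP with a date and reason, and report the endpoint as not assessed.

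The first route costs SAP wording and one model, since the protocol already plans the samples and assays. The second costs a dated entry in the SAP and a line in the report.
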